Official Title: Double-blind Randomized Controlled Trial of Anakinra, Pentoxifylline, and Zinc Compared to Methylprednisolone in Severe Acute Alcoholic Hepatitis

NCT NUMBER: NCT01809132

Protocol approval date: 11/23/2015

The University of Texas Southwestern Medical Center at Dallas Institutional Review Board

Novel Therapies in Severe Acute Alcoholic Hepatitis

1. Study Specific Aims:

Aim 1: Evaluate the effects of corticosteroids versus a combination of interleukin-1 inhibitor plus pentoxifylline plus zinc supplements in patients with MELD \geq 20. Patients will be randomized to receive 28 days of methylprednisolone 32 mg daily OR therapy that includes a combination of anakinra (interleukin-1 receptor antagonist, IL-1 RA) 100mg by subcutaneous injection daily for 14 days PLUS pentoxifylline 400 mg p.o. three times daily for 28 days PLUS zinc supplements (220 mg of zinc sulfate) given orally for 6 months. This combination strategy will treat the acute inflammatory component of the disease (anakinra) and protect against development of hepatorenal syndrome (pentoxifylline), one of the most frequent causes of death in severe AAH. Gut mucosal integrity will be restored (zinc supplements), a critical component in preventing repeated episodes of AAH. The primary outcome will be 6 month mortality rate. Secondary outcomes will be measured at 30, 90 and 180 days. They include change in gut mucosal permeability; changes in the levels of serum endotoxin, IL-1, tumor necrosis factor-1 (TNF1) and other cytokines from baseline; mortality; and change in MELD score.

Aim 2: Document the natural history of severe alcoholic hepatitis. Patients who decline randomization will be offered the option of inclusion in the study prospectively for data collection purposes and research study procedures.

Aim 3: Create a data and tissue biorepository. This biorepository will serve as a national resource for all studies related to acute alcoholic hepatitis. Our research group will use the samples and share with others for future studies on biomarkers for AAH severity/outcome, cost analysis, rationales for new therapies, etc.

2. Background:

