- Alcohol usage in the past 60 days prior to assessment specifically and the pattern of chronic usage.
- Review inclusion and exclusion criteria
- Collection of blood for hematology, coagulation, clinical chemistry to include amylase and lipase, ammonia, and in female patients, a pregnancy test.

- Physical examination, including height, weight (body mass index will be calculated based on these variables), and vital signs (systolic and diastolic blood pressure, pulse rate, respiratory rate and body temperature)
- Ultrasound or cross –sectional imaging of the abdomen. This is standard of care in patients hospitalized with alcoholic hepatitis.

Study treatment:

Patients will be randomized to receive 28 days of methylprednisolone 32 mg daily OR therapy that includes a combination of anakinra (interleukin-1 receptor antagonist, IL-1 RA) 100mg by subcutaneous injection daily for 14 days plus pentoxifylline 400 mg orally three times daily for one month PLUS zinc supplements (220 mg of zinc sulfate) given orally for 6 months.

Assessments at baseline and during study treatment:

Study day 0 – baseline (within 48 hours of study enrollment)

- Complete collection of all baseline history. Review of alcohol use history.
- Complete collection of all indicated standard of care laboratory evaluations (chemistry, hematology, coagulation, urine, microbiology, viral, and TB testing) .
- Ascites evaluation, if present.
- Collection of baseline research testing to include urine, blood, DNA and stool testing.
- Collect prior and concomitant medications.
- Clinical assessment to include vital signs and physical exam details.
- Nutritional assessment with a hand grip dynamometer

Treatment day 1 – time zero (alternatively note this as treatment day one with no time and above as study day 1 baseline)

- Begin continuous AE review and reporting
- Begin subcutaneous injected study medication or placebo injection
- Begin dosing of oral study medications (pentoxifylline 400 mg 3 times daily PLUS zinc sulfate 220 mg once daily)/placebo or oral methylprednisolone/placebo preparation

Treatment day 2:

- Inpatient assessment to include:
 - Review baseline history for changes. Review alcohol intake history.
 - Collection of prior and concomitant medications
 - Clinical assessment including vital signs and physical exam details
 - Collection of blood for clinically indicated laboratory studies.
 - Collection of research laboratory studies including urine and blood.

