Statistical analysis plan: Our primary analysis of this outcome will be the unadjusted log-rank test of the Kaplan-Meier survival estimates for the two treatment groups at a two-sided alpha level of 0.05 with survival censored at 6 months. Secondary analysis will use a Cox proportional hazards regression model (with survival censored at 6 months) to adjust the treatment difference in survival for patient characteristics (e.g., age, gender, time since diagnosis) and other covariates (e.g., ALT, AST, other lab measures). Predictors will be added to the model using reference cell coding, as with the mixed models above. The Cox model generates estimates of the hazard ratio for each factor compared to the reference level; e.g., for male patients vs. female patients, assuming gender = 1 for male and 0 for females, a hazard ratio of 1.25 indicates that males have a 25% higher probability of death overall by 6 months compared to females. We can also add time-dependent covariates to the model, such as ALT levels at 2 and 4 months, to estimate their predictive value for mortality. To assess the fit of the model, we will use Nagelkerke's R² constructed from the ratio of the likelihoods for the fitted model to the intercept only model. As further secondary analysis, we can eliminate the survival censoring

at 6 months and test the overall survival throughout the duration of follow-up.

General analysis plan for experiments with fold change as the outcome: Initial analyses will be descriptive in nature, allowing for investigation of appropriate normalization approaches. Initial comparative analyses of fold-change between treatment groups (or between other groups of interest) will be through a standard two-group t-test at the p=0.05 level with appropriate adjustment for unequal variances. If the fold change data are longitudinal in nature, we will use mixed (random effects) models to estimate the change in fold-change over time. In these models, fold-change at each time point will be the outcome with treatment (or other group indicator) and time as predictors. Additional patient characteristics can be added to the model to create adjusted estimates of treatment (or other group) differences. Mixed models can adjust for the correlation due to measures within patients and due to repeated microarrays at each time point.

References

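### The fold-change analysis does not adjust for the Day 0 level; if it governs the cytokine and endotoxin outcomes, adding log baseline as a covariate would gain precision at no cost

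*Combined protocol and SAP*

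**What the plan says.** The relevant text is the last part of section 13 (Biostatistics), headed "General analysis plan for experiments with fold change as the outcome".

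- **First comparison.** "Initial comparative analyses of fold-change between treatment groups (or between other groups of interest) will be through a standard two-group t-test", to be run "at the p=0.05 level with appropriate adjustment for unequal variances".
- **Longitudinal data.** A mixed model in which "fold-change at each time point will be the outcome with treatment (or other group indicator) and time as predictors".
- **Other covariates.** "Additional patient characteristics can be added to the model to create adjusted estimates of treatment (or other group) differences". This is permissive, and the analyte's own baseline level is not named.
- **Scale and reference.** "Initial analyses will be descriptive in nature, allowing for investigation of appropriate normalization approaches". Neither a log scale nor the reference for the fold change (own baseline, control group or something else) is fixed.

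Aim 1 lists among the secondary outcomes "changes in the levels of serum endotoxin, IL-1, tumor necrosis factor-1 (TNF1) and other cytokines from baseline". Section 3 has these measured in both groups at baseline and at 2, 7, 30, 90 and 180 days. Section 6 provides on study day 0 for "Collection of baseline research testing to include urine, blood, DNA and stool testing", and the schedule of events marks cytokines at Day 0. No other analysis is given for these outcomes in the severe trial.

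**The concern.** Suppose fold change is the ratio of the follow-up level to the patient's own Day 0 level. On the log scale it is then a change score, which is the same as fixing the regression slope of follow-up on baseline at 1. When the true slope is lower, patients with high starting values tend to fall further whatever their treatment. That adds noise to the comparison, and it carries part of any chance difference in baseline between the arms into the estimated effect.

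The listed mixed model does not remove this. When every value is divided by the patient's own Day 0 value, Day 0 equals 1 for everyone, so including it as a response recovers nothing.

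The protocol's mechanistic hypothesis (inflammation driven by gut-derived endotoxin) rests largely on these contrasts, in at most 65 patients per arm. Randomization is stratified by MELD band, not by cytokine or endotoxin level, so chance differences in those levels can occur.

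**Working it through.** **No figure to reproduce.** The documents give no SD, effect size, power or baseline to follow-up correlation for any fold-change outcome.

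**Inputs from the documents:** 65 patients per arm, equal allocation, and assumed 6-month survival of 0.64 and 0.82 (section 13, severe trial). The 0.05 level is taken as two-sided.

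**Assumptions:** fold change relative to own Day 0, log scale, the same SD (sigma) at both times, and rho varied from 0.3 to 0.9.

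**Precision.** Let X be log Day 0 level and Y log follow-up level.

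- Change score: Var(Y - X) = 2 sigma^2 (1 - rho)
- ANCOVA: Var(Y given X) = sigma^2 (1 - rho^2)
- Ratio: (1 - rho^2) / [2(1 - rho)] = (1 + rho)/2

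If the t-test had 80% power, ANCOVA power is Phi[(1.960 + 0.842)/sqrt((1 + rho)/2) - 1.960]. At rho 0.5 this is Phi(2.802/0.866 - 1.960) = Phi(1.275) = 0.899.

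The detectable difference at 80% power, in log-SD units, is 2.802 x sqrt(2v/65), where v = 2(1 - rho) for the t-test and v = 1 - rho^2 for ANCOVA.

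| rho | variance ratio | extra patients the t-test needs | power if t-test has 80% | detectable difference, t-test | detectable difference, ANCOVA |
|---|---|---|---|---|---|
| 0.3 | 0.65 | 54% | 93.5% | 0.58 | 0.47 |
| 0.5 | 0.75 | 33% | 89.9% | 0.49 | 0.43 |
| 0.7 | 0.85 | 18% | 86.0% | 0.38 | 0.35 |
| 0.9 | 0.95 | 5% | 82.0% | 0.22 | 0.21 |

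The extra patients are 1/ratio - 1, for example 1/0.75 - 1 = 33%.

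**Chance imbalance.** Given an observed baseline difference d between arms, the change-score contrast shifts by -(1 - rho)d. One standard error of d is sqrt(2/65) = 0.175 SD. The shift is then 0.123, 0.088, 0.053 and 0.018 SD at rho 0.3, 0.5, 0.7 and 0.9.

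**Simulation.** This used 20,000 trials of 65 per arm with no treatment effect, at rho 0.3, 0.5 and 0.7 and log-SD 0.5 and 1.0.

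- Over all trials, the mean t-test estimate lay between -0.002 and +0.001 and type I error between 0.047 and 0.052.
- In the 10% of trials with the largest imbalance in one direction (about 0.31 SD), the mean t-test estimate at log-SD 1.0 was -0.22, -0.16 and -0.09 SD at rho 0.3, 0.5 and 0.7. Type I error was 14.0%, 12.1% and 8.6%. At log-SD 0.5 it was 12.3%, 10.5% and 8.7%.
- ANCOVA stayed within 0.006 of zero in those same trials.
- The simulated variance ratios were 0.65 to 0.66, 0.76, and 0.85 to 0.86, in line with the formula.

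**Scale.** With log-SD 1.0, rho 0.5 and an effect of 0.5 SD, power was 0.62 for a t-test of the raw ratio, 0.81 for the log change and 0.90 for ANCOVA.

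**Numbers at Day 180.** Average assumed survival is (0.64 + 0.82)/2 = 0.73, so about 65 x 0.73 = 47 patients per arm before dropout. At rho 0.5 the detectable difference is then 0.58 SD for the t-test and 0.50 SD for ANCOVA.

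**The case against.** Several points on the other side stand.

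- **Scope is inferred.** The section speaks of experiments, normalization and repeated microarrays, which suits the genomic and microRNA work at least as well as serum cytokines. If it covers only those, the gap is a different one: the cytokine and endotoxin outcomes have no stated analysis.
- **Baseline is not ignored.** A reader might infer that the plan throws the Day 0 measurement away. Under the own-baseline reading, that value is the denominator of every fold change. Under another reference, the slope-of-1 argument and the (1 + rho)/2 formula do not apply.
- **The test is not biased in general.** A reader might infer that baseline imbalance invalidates the contrast. Arms are randomized equally within MELD bands, so on the log scale the t-test is unbiased on average and its error rate already allows for chance imbalance. The shift exists only conditional on an imbalance. Systematic bias is a concern only for the non-randomized groups that the section also allows to be compared.
- **The t-test is only the initial analysis.** A mixed model with optional covariates follows. That softens the point but does not settle it, because adding baseline is neither required nor named.
- **The gain may be small.** At rho 0.9 the variance falls by only 5%.

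Against this, the same section plans an ANCOVA with baseline MELD for the moderate trial's MELD change, as a secondary analysis. The method is therefore already within the team's stated practice.

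**Conclusion.** The point holds as an inexpensive improvement to a secondary analysis; it does not correct an invalid test. It depends on two readings that the plan leaves open: that the fold-change section governs the cytokine and endotoxin outcomes, and that fold change is relative to the patient's own Day 0 value. On those readings, and with equal log-scale SDs, the planned t-test gives up 35%, 25%, 15% or 5% of its variance at rho 0.3, 0.5, 0.7 or 0.9. The conclusion that a gain exists holds for any rho below 1, but its size rests on an assumed rho and a hypothetical 80% starting power.

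The finding of no average bias applies to randomized patients with both measurements. Late visits exist only for survivors, and baseline adjustment does not resolve that. The primary log-rank analysis of 6-month mortality is not touched.

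**What to change.** Amend the fold-change part of section 13 as follows.

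1. State that it applies to the cytokine and endotoxin secondary outcomes, and define the reference and the scale of fold change.
2. For biomarkers measured at Day 0, analyse log follow-up level by ANCOVA with treatment and log Day 0 level as covariates.
3. For longitudinal data, use a mixed model with treatment, visit, treatment-by-visit and log Day 0 level, and a patient random effect.
4. Report ratios of adjusted geometric means with 95% confidence intervals.

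The covariate should be a true pre-treatment value. A footnote to the schedule of events lets the first gut permeability test fall within the first 28 days for non-ICU patients, so a value taken after dosing has started should not serve as baseline.

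The cost is SAP wording. No new samples or visits are needed.

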4. Criteria for Inclusion of Subjects for Natural History Specimen Collection:

- a. Ability to provide informed consent by subject or appropriate family member
- b. Age between 21-70
- c. Suspected or proven alcoholic liver disease

5. Criteria for Exclusion of Subjects for Natural History Specimen Collection:

- a. Pregnancy; incarceration; inability to provide consent or lack of appropriate family member
- b. Signs of uncontrolled systemic infection: Fever $> 38.0^{\circ}\text{C}$; positive blood or ascites cultures on appropriate antibiotic therapy for >3 days within 3 days of inclusion
- c. Evidence of acute pancreatitis: CT evidence or amylase or lipase $>5 \times \text{ULN}$
- d. Evidence of other liver diseases such as autoimmune hepatitis, primary biliary cirrhosis, primary sclerosing cholangitis, Wilson disease, biopsy proven hemochromatosis, alpha-1-antitrypsin deficiency

Over the entire 6 months study period 387 mL of blood will be drawn, comprising 208 mL for standard of care tests and 179 mL for research studies.

Optional DNA Blood Sample Collection: A biorepository can serve as a national resource for all studies related to acute alcoholic hepatitis. A major goal of the U-01 consortium is to share clinical samples. Our research group will use the samples and share with others for future studies on biomarkers for AAH severity/outcome, cost analysis, rationales for new therapies, etc. Blood and tissue samples will be collected as indicated in the table. Samples for DNA preparation will be shipped to the Cleveland Clinic and specimens will be shipped to those translational sites that are studying biomarkers or pharmacogenomics (U Mass, U Louisville). Specimens will only be identified by the unique study number. De-identified data obtained from the various pharmacogenomics, miRNA and transcriptosome screens will be placed on the website of the U-01 consortium and be available to the U-01 investigators throughout the study.

The amount of blood that would be collected is 8 mL (2 tbspsns) and it will be stored at the Cleveland Clinic Foundation as part of the NIH Tissue and Biorepository for Alcoholic Hepatitis Studies.

7. Sources of Research Material: Specimens: Blood, urine, stool

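### The fold-change analysis plan, which covers microarray data, sets an unadjusted p=0.05 threshold, and the documents contain no multiplicity control

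*Combined protocol and SAP*

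**What the plan says.** The relevant text is the last paragraph of section 13, the general plan for fold-change experiments. It proceeds in three steps.

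1. Description: "Initial analyses will be descriptive in nature, allowing for investigation of appropriate normalization approaches".
2. Comparison of the treatment groups, or of other groups that it does not name, which "will be through a standard two-group t-test at the p=0.05 level with appropriate adjustment for unequal variances".
3. Mixed models for longitudinal data, with treatment and time as predictors. On these it adds: "Mixed models can adjust for the correlation due to measures within patients and due to repeated microarrays at each time point".

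The screens themselves appear elsewhere. Section 6, under the optional DNA blood sample, states: "De-identified data obtained from the various pharmacogenomics, miRNA and transcriptosome screens will be placed on the website" of the consortium. It gives "future studies on biomarkers for AAH severity/outcome" among the uses of the samples. The schedule table in section 6 lists serum micro RNA at Day 0, Day 7, Day 28, 3 months and 6 months. Section 7 includes blood micro RNA, blood DNA and stool microbiome DNA in the research data.

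The adjustments named for fold-change data are for unequal variances, within-patient and repeated-array correlation, and patient characteristics. The documents mention no false-discovery control, Bonferroni or other multiplicity procedure, and no validation set. They do not label these results as hypothesis-generating.

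**The concern.** A 0.05 threshold limits the error of one test. A microarray or miRNA panel yields one fold change per feature, and a two-group t-test on such data is naturally run once per feature. None of the adjustments in the paragraph addresses the number of features. A mixed model handles correlation within a patient, but fitted feature by feature it still gives one treatment test per feature. Several visits and the unnamed extra group comparisons add more tests.

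At stake is the credibility of the biomarker findings that the trial team would report as significant. The repository is meant to support biomarker work well beyond this trial, so false leads would cost specimens and effort in follow-up studies.

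**Working it through.** The documents give no feature count, power or expected number of false positives for these analyses, so there is no stated figure to reproduce.

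**Inputs from the documents.** The per-test level is 0.05 (section 13; sidedness is not stated and is taken as two-sided). There are at most 65 patients per arm (section 13, severe trial). Serum micro RNA has five scheduled visits, so up to four post-baseline ones (section 6 table).

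**Assumptions not in the documents.** The number of features m, the share of features that are truly null π0, the power, and the standardised effect d.

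**Step 1: expected false positives in one comparison.** The formula is 0.05 × number of null features. This expectation holds even if features are correlated.
- 200 null features: 0.05 × 200 = 10
- 1,000: 0.05 × 1,000 = 50
- 20,000: 0.05 × 20,000 = 1,000

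If 1,000 null miRNA features were tested separately at each of four post-baseline visits, the expected number would be 4 × 50 = 200.

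**Step 2: false share of the declared features.** A count does not show whether false positives outnumber true ones. The expected share is π0 × 0.05 / (π0 × 0.05 + (1 − π0) × power), which does not depend on m. At 80% power:
- π0 = 0.80: 0.040 / (0.040 + 0.160) = 20%
- π0 = 0.90: 0.045 / (0.045 + 0.080) = 36%
- π0 = 0.95: 0.0475 / (0.0475 + 0.040) = 54%
- π0 = 0.99: 0.0495 / (0.0495 + 0.008) = 86%

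**Step 3: when the share passes one half.** Setting the two terms equal gives π0 = power / (power + 0.05).
- 80% power: 0.80 / 0.85 = 0.941
- 50% power: 0.50 / 0.55 = 0.909
- 30% power: 0.30 / 0.35 = 0.857

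Deaths and drop-out leave fewer than 65 per arm at later visits, which lowers power. For d = 0.5, power at the 0.05 level is 0.813 with 65 per arm and 0.609 with 40. At π0 = 0.90 the false share then rises from 0.045 / (0.045 + 0.0813) = 36% to 0.045 / (0.045 + 0.0609) = 42%.

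**Step 4: effect of false-discovery control at 5%.** This is approximated by the per-test threshold a that solves a / (π0 × a + (1 − π0) × power(a)) = 0.05. The illustration uses one comparison, m = 1,000, d = 0.8 and 65 per arm.

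| π0 | Unadjusted: false / true positives (false share) | Threshold a | Controlled: false / true positives (false share) |
|---|---|---|---|
| 0.80 | 40.0 / 199.1 (16.7%) | 0.0102 | 8.1 / 195.4 (4.0%) |
| 0.95 | 47.5 / 49.8 (48.8%) | 0.0025 | 2.3 / 46.9 (4.8%) |
| 0.99 | 49.5 / 10.0 (83.3%) | 0.00045 | 0.4 / 8.5 (5.0%) |

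Most true signals are kept in this illustration because d = 0.8 is a large effect. Smaller effects or fewer patients would lose more.

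**The case against.** The strongest reply has four parts.

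First, the paragraph is generic. It never says that testing is feature by feature, it names neither miRNA nor transcriptome, and it would fit a single marker equally well. The schedule table has no transcriptome or microarray row, and pharmacogenomic DNA data are not obviously a fold-change outcome. This stands as a limit on wording: per-feature testing and the link to the screens are inferences. The mention of repeated microarrays is in the paragraph itself, however, so many-feature data are within its scope.

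Second, the t-test is presented as an initial step, with mixed models for longitudinal data, so a separate t-test at every visit is not clearly planned. That is fair, and the four-visit figure above is conditional on it. But the mixed models do not correct across features either.

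Third, a reader might infer that lists of significant features will be published on the consortium website and that later studies will start from them. The documents do not support this. Section 6 promises de-identified data, and investigators who receive data can apply their own error control. The exposure is mainly through the trial team's own reported findings.

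Fourth, these analyses are ancillary, and a protocol may leave omics error control to platform-specific plans. The results are indeed ancillary. But the text does set a significance level for these experiments, and it neither refers to a further plan nor calls the results exploratory.

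**Conclusion.** The point holds in a bounded form. The plan sets an unadjusted 0.05 rule for fold-change experiments that include microarrays, and no multiplicity control appears anywhere in the documents. Applied per feature, the rule declares about 5% of null features different in each comparison.

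A reader might go further and conclude that the significant features would be mostly false. The documents do not establish that, because they give neither the feature count nor the null share. At an assumed 80% power the false share is 20% if 80% of features are null, and it exceeds one half only above about 94% null. With lower power that point comes earlier, at about 91% null for 50% power.

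The weakness touches ancillary biomarker results only. The primary log-rank test of 6-month mortality is unaffected.

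**What to change.** Amend the fold-change paragraph in section 13 as follows.

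- For any platform that measures many features, replace the p=0.05 rule with Benjamini-Hochberg q-values at a false discovery rate fixed in advance, 5% or 10%.
- Define the family per platform, across features, time points and group contrasts. List the other groups to be compared.
- Apply the same control to the treatment and treatment-by-time tests from the mixed models, not only to the t-tests.
- Label any unadjusted result as exploratory, including results for single markers. For example, section 3 has endotoxin, IL-1 and TNF measured at five post-baseline times. Tested separately, that is 3 × 5 = 15 tests, with a chance of at least one false positive of 1 − 0.95^15 = 54% if all are null and independent.

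No new data are needed. The work is SAP wording, a definition of the families before analysis, and a small amount of code. The price is that fewer features are declared significant, and more true ones are missed where effects are modest or later visits are thin. The illustration in the working is for one comparison; the threshold in the full family will depend on the null share across all the tests pooled.
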